#### Graft loss

- Source: Hospitalization CRF
- Occurrence: “Primary reason for hospitalization” = 20 (“Graft loss”)
- Date of event: “Date of admission”

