6.5.6 Premature patient withdrawal from study treatment

Patients *may* voluntarily withdraw from study treatment or study treatment may be discontinued at the discretion of the investigator at any time. Patients must be withdrawn prematurely from the study treatment if any of the following occur:

- premature discontinuation of study drug (see [section 6.5.5](#))
- pregnancy
- graft loss / re-transplantation
- third severe rejection episode (ISHLT 1990 grade \geq 3A resp. ISHLT 2004 grade \geq 2R) with or without hemodynamic compromise or rejection episode requiring change in baseline immunosuppressive therapy according to this protocol or any rejection ISHLT 1990 grade \geq 3A resp. ISHLT 2004 grade \geq 2R within months 6 – 9 **(as assessed by per protocol biopsies)**
- occurrence or detection of severe medical disorder jeopardizing the life of the patient in the immediate future

If such premature withdrawal from study treatment occurs, or if the patient fails to return for visits, the investigator must determine the primary reason for a patient's premature withdrawal from the study and record this information on the Study / Treatment Completion CRF.

Patients may be withdrawn from the study treatment prematurely at the investigator's discretion for one of the following reasons:

1. adverse event(s)
2. abnormal laboratory value(s)
3. abnormal test procedure result(s)
4. unsatisfactory therapeutic effect (e.g. severe rejection)
5. protocol violation
6. administrative problems
7. patient's condition no longer requires study treatment

In cases of recurrent infections serum antibody concentration should be measured; if hypogammaglobulinemia presents as persistent and clinically significant, patients should be examined accurately and appropriate actions should be taken; MPA dose reduction or change of MPA-based immunosuppression should be taken into consideration.

Patients with recurrent pulmonary disorders e.g. cough/dyspnea should as soon as possible be examined accurately for signs of bronchiectasis; MPA dose reduction or change of MPA-based immunosuppression should be taken into consideration.

For patients who are lost to follow-up, the investigator should show “due diligence” by documenting in the source documents steps taken to contact the patient, e.g. dates of telephone calls, registered letters, etc.

Patients who discontinue participation in the trial for any reason will not be replaced.

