The allograft will be presumed to be lost on the day the patient is scheduled for re-transplantation. This will be reported on the End of Treatment CRF if medication is discontinued prematurely and Study Completion CRF. Graft loss / re-transplantation are considered a Serious Adverse Event and must be reported on the Serious Adverse Event Case Report Form, which must be faxed to Novartis.

Major Adverse Cardiac Events (MACE)

Major Adverse Cardiac Event will be defined as one of the following:

- any death
- myocardial infarction
- coronary artery bypass grafting

All major adverse cardiac events will be recorded on the CRF and are subject to expedited reporting as specified in [section 8.1](#).

- **Echocardiogram**

Echocardiograms will be performed as needed for suspected rejection episodes. Results will be recorded on the Echocardiogram CRF.

- **Electrocardiograms (ECG)**

A 12-lead ECG will be written and documented in the CRF with ventricular rate, PQ interval, QRS duration and QT interval.

Additionally, the investigator will assess the following:

heart rate: normal, bradycard, tachycard,
rhythm: eurhythmia, arrhythmia,
block signs: S-A Block,
 AV-Block °I, °II (Wenckebach, Mobitz, Periodic), or °III,
 Interventricular Block (right bundle-branch, left bundle-branch)

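### The SAP counts graft loss only from an admission coded to it and dates it to that admission; the protocol uses other forms and the day of scheduling for re-transplantation, and the change is undeclared

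*SAP*

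**What the plan says.** SAP 5.1.3, under Graft loss, gives a three-line derivation. The form is "Source: Hospitalization CRF". The event occurs when "Primary reason for hospitalization" carries code 20, graft loss. The event date is "Date of admission". The composite component is graft loss or re-transplant, but the SAP gives re-transplantation no derivation of its own.

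Protocol 7.5 defines the same event differently. On timing: "The allograft will be presumed to be lost on the day the patient is scheduled for re-transplantation". On recording: "This will be reported on the End of Treatment CRF if medication is discontinued prematurely and Study Completion CRF", and further: "Graft loss / re-transplantation are considered a Serious Adverse Event and must be reported on the Serious Adverse Event Case Report Form". It does not name the hospitalization form for this endpoint; hospitalization data are described in protocol 7.8, under resource utilization.

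SAP section 4 lists two changes from the protocol: the missing-data methods for the primary variable, and the restriction of non-randomized patients to the run-in period. The graft-loss source and date are not mentioned.

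**The concern.** SAP 2.6.2 analyses treatment failure and each of its components by Kaplan-Meier and log-rank test, from randomization to the first documented date of the event. Both the event indicator and the event date enter the test. A programmer who follows SAP 5.1.3 exactly can leave out a graft loss that the protocol counts, or place it at a different time. SAP 2.6.2 also promises a narrative for every graft loss, which requires every case to be found.

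Protocol sections 1 and 11 expect the CNI-free regimen to match the CNI regimen on outcomes that include graft loss. The comparison therefore has interpretive weight even though it is explorative.

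**Working it through.** There is no planned figure to reproduce. The check sets the two rules side by side and follows individual patients through them.

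| | Protocol 7.5 | SAP 5.1.3 |
|---|---|---|
| What triggers the event | scheduling for re-transplantation | an admission whose primary reason is coded graft loss |
| Event date | day of scheduling | day of admission |
| Forms | End of Treatment (if medication stops early), Study Completion, SAE | Hospitalization only |

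**Does the protocol expect a record without an admission?** Yes. Section 6.5.6 says "Patients must be withdrawn prematurely from the study treatment if any of the following occur", and graft loss or re-transplantation is on the list that follows. The investigator must determine the primary reason and "record this information on the Study / Treatment Completion CRF". Section 7.6 makes graft loss an SAE by definition. Section 6.5.6 also lists allograft survival and hospitalizations as separate items of the Month 18 follow-up. None of this depends on the patient being admitted.

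**What happens to each type of patient?** Deaths have their own derivation in SAP 5.1.3, so the cases that matter most are survivors. Months below are assumed for illustration; time runs from randomization at Month 6.

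1. Scheduled but not admitted by Month 18. If scheduled at Month 15, the protocol gives an event at 15 − 6 = 9 months. The SAP gives no event.
2. Re-transplanted during an admission with another primary reason. Protocol 7.8 names adverse events and treatment of acute rejection among possible reasons. The protocol gives an event; the SAP gives none.
3. Scheduled first, admitted for graft loss later. If scheduled at Month 12 and admitted at Month 16, the protocol gives 12 − 6 = 6 months and the SAP gives 16 − 6 = 10 months.
4. Already in hospital with graft loss as primary reason when scheduled. The SAP date is then the earlier one.

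If both dates fall within the randomized period, the shift cannot exceed 18 − 6 = 12 months.

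**What reaches the composite?** A patient who also meets another component stays in the composite, though possibly at a different date. In the separate graft-loss analysis, a case of type 1 or 2 is lost in any event.

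**How many patients?** The documents give no graft-loss rate and no interval between scheduling and admission. The count may be zero, and the effect cannot be computed.

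**The case against.** The strongest defence is that the SAP merely makes the protocol operational. Protocol 10.1 leaves detail to the SAP, the Kaplan-Meier and log-rank methods are unchanged, and section 4 is meant for changes to analyses. The hospitalization form has a dedicated graft-loss code, and protocol 7.8 asks for all relevant hospitalizations inside and outside the center, so most cases may well be caught. The list of admission reasons in 7.8 is not exhaustive and does not show that graft loss would be coded elsewhere. All of that is fair, and it rules out calling the form unsuitable. It does not remove the conflict: the SAP drops every form the protocol names and replaces the date rule, which goes beyond filling in detail.

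A second defence concerns the alternative sources. A reader might infer that the Study Completion form would settle the matter, because the SAP already uses it for death and loss to follow-up. The documents do not go that far. Those two events end follow-up, whereas a survivor with graft loss leaves study treatment but is still followed to Month 18. No passage shows a graft-loss code on that form, and it too may hold only one primary reason. Nor is SAE data shown to be in the analysis database; protocol 8.1 describes a faxed form. No form is shown to capture the scheduling date. These limits stand, and they are why the remedy needs reconciliation and a fallback date.

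A reader might also infer that the derivations of biopsy-proven rejection and of rejection with hemodynamic compromise have the same fault. That is not supported. Protocol 7.5 itself has biopsy results recorded on the visit biopsy form that the SAP uses, and the hemodynamic item depends on forms that are not in the documents.

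**Conclusion.** The conflict is real and rests on the text alone: a different trigger, different forms, a different date and no declaration. It is worth correcting because the SAP states a rule that departs from the protocol's definition, and following it can miss or misdate a survivor's event.

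The reach is limited. Treatment failure and its components are secondary and explorative (SAP 2.6.1), and the primary GFR analysis is untouched. A reader might infer that the rule biases the comparison towards one regimen, or that events were in fact lost. The documents support neither: a missed event could fall in either arm, dates can move either way, and the number affected is unknown and may be zero. Confidence is high for the mismatch; no size can be given for its effect.

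**What to change.** Before database lock, revise the graft-loss entry in SAP 5.1.3 as follows:

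- Count graft loss or re-transplantation if it is recorded on the End of Treatment, Study Completion or Hospitalization form, or on the SAE form by reconciliation against the safety records.
- Date the event by the day of scheduling for re-transplantation where that is recorded. Otherwise use a stated fallback, such as the earliest documented date across these forms.
- List in SAP section 4 any remaining departure from protocol 7.5, including the fallback date.

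The SAP's document history places it before database lock, so the change is still timely. The cost is SAP wording, programming and reconciliation across forms. Whether the existing forms hold everything needed cannot be confirmed from the documents; the fallback covers a missing scheduling date.

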#### Loss to follow-up

- Source: Study completion CRF
- Occurrence: “Primary reason for premature discontinuation” = 8 (“Lost to follow-up”)
- Date of event: “Last known date subject took study drug”

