6.5.5 Study drug discontinuation

In case of platelet count < 50,000/mm³, leukocyte count < 3,000/mm³ or neutrophil count < 1,500/mm³, at the discretion of the investigator, MPA medication dose may be reduced by half, or eliminated completely until the event resolves. In case of dose reduction, MPA should be reduced according to the guidelines given in [Appendix 5](#). Everolimus should be continued on a stable dose level and reduced only if the symptoms do not respond to the reduction of the MPA dosage.

In case of elevated cholesterol and/or triglyceride levels, lipid lowering medications should be maximized. If the elevation persists, the dosing of Everolimus should be adjusted following the recommendations given in [Appendix 5](#).

Dose reduction may be performed for those patients with other moderate/severe AEs according to the investigator's judgment. Also in these cases, the medication doses can be reduced by half or interrupted completely until event resolves.

If the MPA or Everolimus medication is interrupted for more than 2 weeks during the run in phase (Month 3 to Month 6 post Tx) or for more than 4 consecutive weeks or more than 8 cumulative weeks within the 12 months study treatment, discontinuation of the respective medication should be considered and the patient withdrawn from study treatment.

Patients who discontinue study drug before completing the maintenance period at Month 18 post Tx should be scheduled for a visit as soon as possible, at which time all of the assessments listed for the final visit (Month 18) will be performed. Month 18 assessments should be repeated at the initially planned timepoint, 18 months post transplantation.

At a minimum, all patients who discontinue study drug, including those who refuse to return for a final visit, will be contacted for safety evaluations during the 30 days following the last dose of study drug.

Patients who discontinue study drug should be considered withdrawn from the study only after the final visit assessments (month 18 post Tx) are performed or when it is clear that the patient will not return for these assessments.

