All patients who prematurely discontinue study treatment should still attend the final visit at Month 18 post transplantation to obtain follow up information on rejection episodes, allograft and patient survival, hospitalizations, malignancies and immunosuppressive medication.

The CRFs Study Completion Page should be completed at month 18 or earlier if the patient can no longer be followed, e.g. due to death, withdrawal of consent, or loss to follow-up.

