#### Last contact:

Last date a contact with the patient is documented, e.g. date of study visit, telephone call, letter, etc.

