#### **2.6.2      Statistical hypothesis, model, and method of analysis**

Event data:

Event rates were estimated using the Kaplan-Meier method to handle patients who discontinue the treatment prior to suffering from an event adequately. Time to event was defined as the time from date of randomization to the first documented date of the event. The two groups were compared using the log-rank test.

This procedure was applied for the composite endpoint of treatment failure and each of its components, as well as MACE and each of its components.

Narratives including relevant medical information were provided for each biopsy proven acute rejection, graft loss, or death.

Tolerability:

Analyses of renal function as determined by other calculations (serum creatinine, glomerular filtration rate (GFR, Cockcroft-Gault)) were evaluated in the same manner as described for the primary outcome measure.

The creatinine slope (1 / serum creatinine versus time) was determined from all assessments between Month 6 and Month 18 (both visits included) using a linear regression model. These slopes were compared with a two-sided Wilcoxon ranksum test between the treatment groups.

Additionally, tolerability of study medication was assessed from the rate of patients who withdraw prematurely from study medication or in whom study medication had to be converted to another immunosuppressive regimen due to abnormal laboratory results, adverse events, or toxicity. The frequency distribution of these reasons was presented with absolute and percent values. The most frequent reasons (total  $n \geq 5$ ) for discontinuation and/or conversion as well as the total number of patients who are affected by such intolerance of study medication were compared between the two treatment groups using the exact Fisher test.

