#### **Treatment failure**

Treatment failure was defined as a composite endpoint of biopsy proven acute rejection of ISHLT 1990 grade  $\geq 3A$  (ISHLT 2004 grade  $\geq 2R$ ), acute rejection episodes associated with hemodynamic compromise, graft loss / re-transplant, death, loss to follow up (at least one condition must be present).

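### The SAP dates loss to follow-up at the last study-drug intake, which is too early for patients who stop drug, have later documented contact and are then lost

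*SAP*

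**What the plan says.** SAP 5.1.3 (Treatment failure) makes loss to follow-up one of the conditions that by itself turns a patient into a treatment failure. The entry for loss to follow-up takes the event from the Study completion CRF and gives its date as "Last known date subject took study drug". SAP 2.6.2 then states: "Time to event was defined as the time from date of randomization to the first documented date of the event". Kaplan-Meier curves and log-rank tests follow for the composite and for each component.

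SAP 2.1.1 also defines a last contact: "Last date a contact with the patient is documented, e.g. date of study visit, telephone call, letter, etc". The loss-to-follow-up entry does not use it.

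The protocol separates stopping drug from leaving the study. Section 6.5.5 says: "Patients who discontinue study drug should be considered withdrawn from the study only after the final visit assessments (month 18 post Tx) are performed", or once it is clear that the patient will not come back for them. Section 6.5.6 adds: "All patients who prematurely discontinue study treatment should still attend the final visit at Month 18 post transplantation". The same section has the Study Completion page filled in at Month 18, or earlier if follow-up is no longer possible. Drug stop alone does not trigger it.

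**The concern.** The last dose is not the date on which a patient is lost. If contact continues after the last dose, the SAP records a failure on a day when the patient was still being followed. This has two consequences.

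- Event times are too early in the composite and in the loss-to-follow-up component.
- A rejection or graft loss that occurs between the last dose and the loss is no longer the first event in the composite, because the loss carries the earlier date.

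The shift is larger in whichever arm has more early stopping followed by later loss, so it need not cancel between arms. The documents do not say which arm that would be.

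**Working it through.** No sample size, power or event count stated in the plan depends on this date, so there is no figure to reproduce. The check compares the texts and then bounds the effect.

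**1. How each component is dated (SAP 5.1.3)**

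| Component | Event date |
|---|---|
| Biopsy-proven acute rejection | Biopsy |
| Rejection with hemodynamic compromise | Biopsy |
| Graft loss | Hospital admission |
| Death | Death |
| Loss to follow-up | Last study-drug intake |

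Only loss to follow-up is tied to drug exposure.

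**2. How long the gap can be**

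The randomized period runs from Month 6 to Month 18 (SAP 5.1.1), so the ceiling is 18 − 6 = 12 months. After drug stop, Protocol 6.5.5 and 7.1 explicitly provide a visit as soon as possible, a safety contact within 30 days and a repeat assessment at Month 18. A patient who attends Month 18 is not lost. The explicitly scheduled contacts therefore give a gap of about one month. A longer gap needs further contacts or SAE documentation, which Protocol 7.1 continues until 30 days after study participation ends.

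The gap also depends on what counts as study drug: everolimus only in Protocol 10.4.1, but also cyclosporin, tacrolimus and MPA in SAP 2.1.1.

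**3. Who is affected**

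Only patients who stopped drug, had later documented contact and were then lost. For someone lost while still on drug, the last dose and the last contact nearly coincide. The number affected is at most the number lost, which the documents do not give.

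**4. Illustration**

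From the documents: 162 randomized 1:1 (SAP 1.1), so about 162/2 = 81 per arm, and a 12-month window. Assumed: 12 other failures per arm spread evenly over the window, 2 lost in the CNI arm and 6 in the CNI-free arm, last dose 1 month after randomization, no other censoring.

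Failure-free proportion at Month 18, under either date:
- CNI: 1 − (12 + 2)/81 = 0.827
- CNI-free: 1 − (12 + 6)/81 = 0.778

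Restricted mean failure-free time, used here only to measure the shift, rises by (number lost × gap)/81 when the loss is moved from last dose to last contact:
- CNI, 6-month gap: 2 × 6/81 = 0.15, from 10.84 to 10.99 months
- CNI-free, 6-month gap: 6 × 6/81 = 0.44, from 10.30 to 10.74 months
- Difference between arms: 10.84 − 10.30 = 0.54 becomes 10.99 − 10.74 = 0.25 months

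Log-rank test, chi-square = (O − E)²/V on 1 degree of freedom:

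| Lost (CNI, CNI-free) | Gap removed | p, last dose | p, last contact |
|---|---|---|---|
| 2, 6 | 1 month | 0.409 | 0.414 |
| 2, 6 | 6 months | 0.409 | 0.442 |
| 0, 6 | 1 month | 0.199 | 0.204 |
| 0, 6 | 6 months | 0.199 | 0.231 |
| 4, 8 | 6 months | 0.434 | 0.467 |
| 4, 4 | 6 months | 1.000 | 1.000 |

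With 10 other patients censored per arm, the Month 18 Kaplan-Meier estimate moves by less than 0.01 in every setting tried. The largest shift was 0.739 to 0.731 (8 lost, last dose at 3 months, last contact at 9 months after randomization).

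**The case against.** The strongest defence is that the SAP follows an on-treatment convention. SAP 2.1 and 5.1.1 say that, for early discontinuers, the last information under study treatment is analyzed. SAP 2.6.2 presents Kaplan-Meier as the way to handle patients who stop treatment before an event. On that reading, dating a loss at the last dose is coherent. Moving that date alone could even place the loss after the patient's own censoring time.

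This does not rescue the rule. The SAP sets no on-treatment cut-off for the other components, which carry their own dates, and gives no censoring date for event-free patients. It does show that the loss date and the censoring date have to be settled together.

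A second objection stands in part. Off-drug time is thinly documented. MACE recording ends 30 days after the last dose (Protocol 7.1). No biopsy is clearly scheduled between the discontinuation visit and Month 18. Most acute rejections are exempt from SAE reporting (Protocol 7.6). A reader might infer that the SAP discards months of documented event-free follow-up. The documents do not support that: such time may be free of recorded death or graft loss, but it is not reliably free of rejection.

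Third, a displaced rejection or graft loss is not lost to the trial. It keeps its date in its own component analysis, and the patient is a failure in the composite either way. This stands.

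**Conclusion.** The rule gives the wrong event time for lost patients whose documented contact continued after the last dose, and it can change which event comes first in the composite. Failure counts by Month 18 are unchanged. The composite is secondary and analyzed in an exploratory way (SAP 2.6.1), and the primary GFR analysis is not touched.

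The size is probably small. With the one-month gap that the explicit schedule supports, the log-rank p moves by about 0.005 on the assumed inputs. With a six-month gap for every lost patient and unequal losses, it moves by about 0.03. These figures rest on assumed numbers of losses and failures.

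A reader might assume a loss rate of 3% to 5%, giving 0.03 × 162 = 4.9 to 0.05 × 162 = 8.1 patients, and treat all of them as misdated by most of a year. The documents support neither step. They give no loss rate, patients lost while on drug are hardly affected, and 12 months is a ceiling rather than a typical gap.

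**What to change.** In SAP 5.1.3, set the loss-to-follow-up event date to last contact as defined in SAP 2.1.1, and specify the last contact at which the patient's status was documented. The qualifier matters because the SAP definition lists calls and letters, and Protocol 6.5.6 has sites record attempts to reach lost patients; an unanswered attempt should not count.

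In SAP 2.6.2, state the censoring date for event-free patients in the composite and use the same follow-up cut-off.

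The cost is one line in each section and no new data, provided contact dates are recorded, as the SAP definition presumes. The small downside is that rejection and MACE are less completely documented after drug stop, so the last-dose dating can be kept as a sensitivity analysis.
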